2.1 Primary Objectives

The objective of this study is to examine a novel approach to improving the quality of care inpatients receive if they use tobacco (oncology and general inpatients).

Specific Aim 1: *Assess whether including a standing order for prescription and management of varenicline (TUT Service+VM) within the inpatient clinical workflow for cancer and non-cancer patients identified as current smokers will significantly increase TUT engagement rates compared to current standard of care (TUT Service alone). Hypothesis:* Observed treatment engagement rates will be higher among clinicians exposed to TUT Service+VM than observed in clinicians exposed to TUT Service alone.

Specific Aim 2: *Assess whether clinicians exposed to the TUT Service+VM condition will be more effective at guiding reluctant patients toward TUT engagement than clinicians exposed to the TUT Service alone condition. Hypothesis:* Rates of important TUT behaviors (e.g. treatment initiation, quit attempts, and others) observed among smoking patients of clinicians exposed to TUT Service+VM will be higher than those than observed among smoking patients of clinicians exposed to TUT Service alone.

Specific Aim 3: *Assess implementation preferences and barriers influencing effectiveness of usual care tobacco use treatment (TUT Service) + varenicline management (VM) applied within the cancer center. Hypothesis:* Oncology specialists exposed to the TUT Service + VM condition will identify key facilitators and barriers to the implementation of the TUT Service + VM condition that can help guide subsequent dissemination efforts.

The goal of this study is to determine if the default for a varenicline order increases clinician referral to TUTS and/or the treatment of tobacco use. At this point, many clinicians are turning the referral order off and patients are not receiving treatment for tobacco use. A default to prescribe treatment may help override barriers to both. While we are focused on cancer inpatients, we will assess the impact of the varenicline management intervention on cancer and non-cancer patients.

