Insights gained from this project form the basis of subsequent clinical trials assessing efficacy of novel implementation approaches improving uptake of evidence-based tobacco use treatment within the inpatient clinical setting. This study is significant because the model for promoting physician behavior change is simple and pragmatic yet has the potential to significantly impact patient survival and morbidity. The study builds on previous observations made through NCI and C.U.R.E. investments, expanding our understanding of novel pharmacologic approaches to tobacco cessation.

3 Study Population and Duration of Participation

The study will be conducted within PPMC in the University of Pennsylvania Health System (UPHS). Participants will be hospitalist and attendings in the Department of Medicine who provide care for inpatients with a cancer diagnosis at PPMC. This study will recruit individuals age 18 or older only. Children under age 18 will not be eligible for this trial.

We plan to derive a sample of 52 clinicians from the available pool of several hundred eligible PPMC clinicians.

No data are to be collected from the patients aside from routinely collected patient-level data regarding tobacco treatment use once patients are referred to [name] tobacco treatment program; patient data are available in the EHR. If clinicians place the referral order (which is already in EPIC) to [name] smoking cessation service, we collect standard information concerning smoking behavior that is standard clinical information, not research data (e.g., use of smoking cessation treatments, quit attempts). No patient data will be collected outside of what is available in the EHR (for clinicians in the study) or what is collected clinically when patients contact the cessation program from the clinician's referral. All patients receiving care from eligible clinicians will be assessed in this study as described above, those with or without cancer, so that we can test the impact of the intervention for cancer inpatients as well as for those inpatients without a cancer history.

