5.4 Inclusion of Non-cancer Patients

After testing the logic of the usual care intervention and the Novel BE intervention, it was determined that these two groups were being treated differently. In the usual care intervention, clinicians would receive the standard TUT Service BPA for all patients, regardless of cancer status. However, in the Novel BE intervention, the clinicians would receive the TUTS + VM BPA for their patients with a cancer history but would also be exposed to the standard TUT Service BPA for their patients without a cancer history. To ensure that these two groups are experiencing the same treatment, we are altering the study logic so that the clinicians randomized to the study Novel BE intervention will be exposed to the TUTS + VM BPA regardless of a patient's cancer status. This will also allow us to test the effect of the intervention on all inpatients, on non-cancer in-patients, and on just cancer inpatients. This change simplifies the system and expands our ability to test the impact of the intervention on differing in-patient populations.

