6.1 Sample Size and Power Determination

Engagement rates are our primary measure of effect. Given that our initial educational intervention was able to change absolute engagement rates by approximately 20%, we assume that a CDS intervention would need to accomplish an equivalent amount of change to be clinically relevant. There are over 1000 BPA activations annually, resulting in approximately 600 TUT Service referrals per year (Engagement rate ~ 60%). To detect improvement in Engagement rate to 80%, with 80% power and a significance level of $p=0.05$, we need to enroll 24 clinicians to each arm. Retention: Because of project nature, we assume drop-out will be minimal (<10%) after enrollment; 26 subjects per arm ensures power.

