6.2 Statistical Methods

For Aims 1 and 2, rate comparisons between the two groups will be performed using Chi-square. We will examine the impact of the intervention on tobacco treatment rates across cancer inpatients, non-cancer in-patients, and all in-patients.

7 Safety and Adverse Events

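### Separate chi-square tests in cancer, non-cancer and all inpatients, with no arm-by-cancer interaction, cannot show whether the effect differs by cancer status

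*Combined protocol and SAP*

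**What the plan says.** Section 6.2 is the whole analysis plan for Aims 1 and 2. Its method is that "rate comparisons between the two groups will be performed using Chi-square", and its populations follow in the next sentence: "We will examine the impact of the intervention on tobacco treatment rates across cancer inpatients, non-cancer in-patients, and all in-patients".

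Section 5.4, explaining why non-cancer patients were added, says the change lets the study "test the effect of the intervention on all inpatients, on non-cancer in-patients, and on just cancer inpatients". Section 3 gives the same purpose: "so that we can test the impact of the intervention for cancer inpatients as well as for those inpatients without a cancer history".

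On which population comes first, the signals are mixed. Aim 1 in section 2.1 is written for cancer and non-cancer smokers together. Section 4.2 counts, for its ordering and referral rates, all patients in each arm whose alert fired. Section 6.1 makes one power calculation, without subgroups. Yet section 2.1 also says "While we are focused on cancer inpatients, we will assess the impact of the varenicline management intervention on cancer and non-cancer patients".

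Nowhere do the documents give an interaction or heterogeneity test, subgroup power, an expected cancer share, a multiplicity rule, or a rule for reading subgroup results that disagree.

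**The concern.** A two-arm chi-square within a subgroup asks whether the effect there is distinguishable from zero. It does not ask whether the effect differs between subgroups. With unequal subgroup sizes, the same true benefit can easily be significant in the larger group and not in the smaller.

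This matters because cancer inpatients are the population of main interest, and section 1 says it is unknown whether this type of intervention carries over to inpatient oncology. If cancer patients are the smaller group, a non-significant cancer result beside a significant non-cancer one invites the conclusion that varenicline management does not work in oncology. The planned tests could not support that conclusion. If non-cancer patients are the smaller group, the same risk runs the other way.

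**Working it through.** **The plan's own figure.** Section 6.1 states 24 clinicians per arm for 60% versus 80% with 80% power at 0.05. The usual two-proportion formula gives 82 independent units per arm (two-sided), so 24 is not reproduced. That is a separate matter and nothing below depends on it. No subgroup or interaction figure is stated.

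**Inputs.**
- From the documents: control rate 60%; planned effect +20 points; alpha 0.05 (taken as two-sided); 26 clinicians per arm; over 1000 alerts a year (all section 6.1); 18 months of data (section 3.1).
- Assumed: all those alerts belong to the study clinicians, so 1000 × 1.5 / 2 = 750 per arm; cancer share 10% to 30%; ICC 0 to 0.05; the same true effect in both subgroups; a smaller effect of 10 points as a comparison.

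**Step 1: no clustering.** With n alerts per arm in a subgroup, difference d and mean rate p̄,

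power = Φ{ [d − 1.96 √(2p̄(1−p̄)/n)] / √[(p₁(1−p₁)+p₂(1−p₂))/n] }.

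For 60% versus 70% at a 10% cancer share:
- Cancer, n = 75: (0.10 − 1.96 × 0.0779) / 0.0775 = −0.68, power 0.248.
- Non-cancer, n = 675: (0.10 − 1.96 × 0.0260) / 0.0258 = 1.90, power 0.971.
- P(non-cancer significant, cancer not) = 0.971 × (1 − 0.248) = 0.73.

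| Effect | Cancer share | n per arm, cancer / non-cancer | Power, cancer | Power, non-cancer | Discordant |
|---|---|---|---|---|---|
| 10 points | 10% | 75 / 675 | 0.248 | 0.971 | 0.73 |
| 10 points | 20% | 150 / 600 | 0.442 | 0.954 | 0.53 |
| 10 points | 30% | 225 / 525 | 0.605 | 0.926 | 0.37 |
| 20 points | 10% | 75 / 675 | 0.767 | 1.000 | 0.23 |
| 20 points | 20% | 150 / 600 | 0.969 | 1.000 | 0.03 |
| 20 points | 30% | 225 / 525 | 0.997 | 1.000 | 0.003 |

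**Step 2: the planned test with clustering.** The same clinicians treat both groups, so the two subgroup results are correlated and the product above no longer applies. Plain chi-square was therefore simulated with clinician-level rates shared across both subgroups. At shares of 10%, 20% and 30%:
- 10-point effect: 73%, 53% and 38% discordant at ICC 0; 64%, 46% and 33% at ICC 0.05.
- 20-point effect: about 25%, 3-5% and 1% or less over the ICC range.

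The clustered 10-point figures move by up to about 3 points with the details of the simulation.

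**Step 3: any positive result under the null.** At ICC 0, at least one of the three overlapping tests is positive in about 11% of trials. At ICC 0.05 it is about 27%. Most of the excess is clustering: with 750/26 = 28.8 alerts per clinician the design effect is 1 + 27.8 × 0.05 = 2.39, so the all-inpatient test alone rejects with probability P(|Z| > 1.96/√2.39) = P(|Z| > 1.27), about 20%.

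**Step 4: what an interaction test could detect.** Without clustering, at 60% versus 80%, the smallest difference in effect detectable with 80% power is 2.80 × √(0.40/n_c + 0.40/n_nc), where n_c and n_nc are the cancer and non-cancer alerts per arm:
- 10% share: 2.80 × 0.0770 = 21.6 points.
- 30% share: 2.80 × 0.0504 = 14.1 points.

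If the true benefit were 10 points in non-cancer and none in cancer, SE = √(0.48/n_c + 0.45/n_nc) and power = Φ(0.10/SE − 1.96), giving about 22%, 36% and 45% at shares of 10%, 20% and 30%.

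**The case against.** - **The primary population is implied.** Aim 1, the per-arm denominators and the single power calculation all point to all inpatients. This stands. A reader might infer that the plan leaves the primary population wholly open, but the gap is only that it is not labelled, and the stated focus on cancer inpatients blurs it. Once it is labelled, the any-of-three error rate matters much less.
- **No difference between subgroups is claimed.** The documents ask for the effect in each population and never say that the effects will be compared. Estimating within each is legitimate, especially in a study that section 4.1 calls a pilot. This also stands: the risk lies in how discordant results would be read, and the plan neither commits the authors to a wrong reading nor guards against one.
- **The large percentages use half the planned effect.** This is right. At 20 points the risk is material only at a cancer share of around 10% or less, unless clustering is stronger than assumed here.
- **An interaction test would rarely settle the question.** Step 4 bears this out. It is a reason to report intervals. It does not make separate p-values a valid comparison.

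**Conclusion.** The point holds as an improvement to the analysis. The method in section 6.2 cannot show whether the effect differs by cancer status, and the primary population should be stated outright.

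The size of the risk depends on two unknowns. With the same 10-point benefit in both groups, misleading discordance is common: about 64-73%, 46-53% and 33-38% at cancer shares of 10%, 20% and 30%. At the planned 20 points it is about 25%, 3-5% and 1% or less. With equal subgroup sizes and no clustering it falls to 15% for 10 points and about zero for 20. All of this rests on the assumed 750 alerts per arm, ICC of 0 to 0.05 and cancer share. The annual alert count in section 6.1 is not tied to the 52 clinicians.

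Two stronger readings are not supported. The plan does not say that it will declare the intervention ineffective in cancer patients. Nor can the inflated false-positive rate be put down mainly to three populations: about 11% applies only without clustering, and the rise to about 27% at ICC 0.05 comes mostly from chi-square ignoring the clinician, which is a separate issue.

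**What to change.** In section 6.2:

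1. Label the all-inpatient comparison as primary and the cancer and non-cancer results as subgroup analyses.
2. Replace the separate subgroup chi-squares with one model that accounts for clustering by clinician (GEE or mixed logistic), with arm, cancer status and arm × cancer.
3. Report the effect in each subgroup and the interaction, all with confidence intervals. State the scale: a logistic interaction is a ratio of odds ratios, so give model-based rate differences beside it.
4. Base any claim that the effect differs by cancer status on the interaction alone, and say that a non-significant interaction is not evidence of equal effects.

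The cost is low. Cancer history is already on the section 8.1 list of data collected, so no further patients, visits or variables are needed. The change does replace chi-square with a regression, since the present plan has no model to which a term could be added. Its limit is power: the smallest detectable difference is about 22 points at a 10% cancer share and 14 at 30%, before any allowance for clustering. The intervals will therefore carry most of the information.

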7.1 Data Safety Monitoring Plan (DSMP)

Because of the nature of the project, and the minimal risk to participant privacy, we do not plan to constitute a formal Data Safety Monitoring Board. However, oversight and evaluation will be accomplished using standard University procedures for safety monitoring. The specific elements of our oversight plan are as above: 1) all project staff will complete certification in the protection of research participants; 2) the principal investigator will supply the IRB with annual progress reports prepared for CURE as specified, or more frequently as determined by the IRB, which may in turn suspend, terminate or restrict the study as appropriate; 3) any serious adverse events will be reviewed in real time by the PI

and reported to the IRB as required; and 4) the PI will inform CURE reviewers of any oversight actions taken by the IRB.

7.2 Internal Monitoring and Auditing

The study will be monitored by the PI and regulatory committees at Penn (i.e., IRBs, OHR). The following monitoring activities will be conducted according to standard operating procedures. These activities will be performed in association with database auditing and facilities monitoring by the Penn OHR and/or study personnel.

Initial Assessment Monitoring: Penn OHR will conduct a manual review of source documents and Case Report Forms (CRFs) for a random subset of participants enrolled in the study. This inspection is the visual comparison of source documents to CRFs in a quantitative assessment of accuracy based on the number of data fields. A brief, internal report will be generated to describe findings. If the data are less than acceptable, additional cases are requested, with appropriate counseling/training for staff.

Protocol Monitoring: Protocol monitoring includes a survey of those activities that are associated with protocol adherence such as study visit deviation and violation of inclusion/exclusion criteria. A specific protocol monitoring plan will be used. All accrued cases will be subjected to protocol monitoring throughout the duration of the trial.

Database Auditing: [name] and the RA will review data entered into the database versus that recorded on the CRFs. All accrued cases will be subjected to database auditing throughout the trial. Depending on the data management findings, re-training will be provided, should problems such as increased errors be detected.

Data Auditing: [name] and the RA will review safety data recorded on the CRF versus that contained on the actual source document (patient chart, EHR). All accrued cases will be subjected to auditing throughout the duration of the trial. A Regulatory Binder Review by OHR will include the following essential documents: IRB Protocol, Amendment Approvals, IRB Closure Letter, List of Authorized Signatures, Laboratory Certifications, Protocol and Amendment Signature Pages, Financial Disclosure Questionnaires, and Monitoring Log. Additional monitoring by OHR may include: source documentation verification; adverse event documentation; and facility assessment.

Data Security: Using network firewall technologies, the database will prevent the three major sources of data security problems: unauthorized internal access to data, external access to data, and malicious intent to destroy data and systems. Controlled user access will ensure that only appropriate and authorized personnel are able to view, access, and modify trial data. All modifications to data will document user access and data associated with the modification, as well as values prior to modification.

IRB Monitoring: The protocol will be reviewed by the Penn IRB and will only be implemented after successful approval from the IRB. Annual reporting and auditing will be conducted by the IRB. All procedures will be approved by the IRB. A protocol-specific Data Safety Monitoring Board will not be used for this study since it is not a clinical trial. The Penn IRB will ensure participant safety and data integrity.

Evidence of Training in Human Subject Research: All personnel working on this project will be required to review the protocol, complete training in the protection of human subjects (developed and implemented by the Penn IRB), and undergo training.

7.3 Reporting of Adverse Events and Unanticipated Problems

The Principal Investigator will promptly notify the Penn IRB of all on-site unanticipated, Adverse Events that are related to the research activity. Other unanticipated problems related to the research involving risk to subjects or others will also be reported promptly. Written reports will be filed using the HS-ERA and in accordance with the Penn IRB timeline of 10 working days.

8 Study Administration, Data Handling and Record Keeping

8.1 Confidentiality

The Data Management System has set up several safeguards to prevent unauthorized access to study data. An automatically generated index number is assigned to a clinician subject's study identification number (unique for clinicians). A linked subject identification table is created for the storing of subject name, address and telephone contact information. This table uses the automatically generated index number rather than the study identification number. The master subject map and subject identification information tables are maintained in a separate database. Using this method, no identifying subject information is directly linked to medical information or other study data. For our multi-site trials, we have long-established protocols to guard against improper use of hard copies of data (e.g., locked files, numeric coding procedures). The present research team has not experienced the unauthorized use of study data. A web-based data collection procedure will minimize the possibility of loss of privacy or confidentiality.

How will confidentiality of data be maintained? Check all that apply.

- Paper-based records will be kept in a secure location and only be accessible to personnel involved in the study.
- Computer-based files will only be made available to personnel involved in the study through the use of access privileges and passwords.
- Prior to access to any study-related information, personnel will be required to sign statements agreeing to protect the security and confidentiality of identifiable information.
- Whenever feasible, identifiers will be removed from study-related information.
- A Certificate of Confidentiality will be obtained, because the research could place the subject at risk of criminal or civil liability or cause damage to the subject's financial standing, employability, or liability.
- A waiver of documentation of consent is being requested, because the only link between the subject and the study would be the consent document and the primary risk is a breach of confidentiality. (This is not an option for FDA-regulated research.)
- Precautions are in place to ensure the data is secure by using passwords and encryption, because the research involves web-based surveys.
- Audio and/or video recordings will be transcribed and then destroyed to eliminate audible identification of subjects.
- Other (specify):

To protect participant confidentiality, only the research team outlined in HSERA will have access to review identified research records. Confidentiality will be protected to the fullest extent allowable under the law.

If any data needs to be transmitted, it will be done through a Penn-approved secure encrypted file transfer solution as is described Penn IRB's Guidance on Electronic Data Protection Requirements for Research Involving the Use of PHI. Records will not be released without the participant's consent unless required by law (e.g., imminent risk of harm to self suspected) or court order. When results of the research are presented at scientific meetings or published, no identifying information will be included.

All identifiable data, including the master list linking identifiers to the ID number and recordings, will be destroyed in 2028, seven years after the award period ends.

The following personal health information will be collected as part of this study:

1. Name
2. Address
3. Date of Birth
4. Phone number(s)
5. Electronic mail address
6. Cancer History
7. Medical Record Number
8. Tobacco Use History

For patient data collected from electronic medical records, as soon as patient data is received by the study staff, all identifiers will be destroyed and replaced with an identification number unique for patients. Using this method, no identifying subject information is directly linked to medical information or other study data.

